5.2 Dose Modifications and Dosing Delays

Dose modification guidelines for pembrolizumab-related AEs during the adjuvant period are provided in Table 7. Dose modification guidelines for pembrolizumab-related AEs during the neoadjuvant period do not apply as only a single dose of pembrolizumab will be administered.

Vactosertib dose reduction based on treatment-related adverse events observed is permitted.

According to the dose levels in Table 6, participants who receive vactosertib below the initially assigned treatment level (200 mg QD or BID) due to vactosertib-related AEs, will have the option to re-escalate to the assigned vactosertib dose if AE(s) resolves to baseline and does not recur for at least 3 consecutive weeks (one treatment cycle).

For the optional adjuvant treatment phase, participants who experience the following drug-related toxicities may escalate to dose level 0 based on the judgement of the investigator:

- Grade 1 or 2 Hematologic Toxicity
- Grade 1 non-hematologic toxicity and/or other drug related toxicities.
- Grade 1 ALT or AST elevation possibly related with total bilirubin <2x ULN

If a Grade 2 or lower vactosertib treatment-related toxicity is experienced but not specified, above dose escalation could be considered after discussions with MedPacto.

If a participant experiences several adverse events and there are conflicting recommendations, the investigator should use the recommended dose adjustment that reduces the dose to the lowest level or if warranted, discontinues therapy.

Table 6 Vactosertib Dose Modification

Neoadjuvant Treatment Phase		Optional Adjuvant Treatment Phase	
Treatment Level	Vactosertib Dose	Treatment Level	Vactosertib Dose
0	200 mg QD	0	200 mg BID
-1	100 mg QD	-1	200 mg QD
-2	100 mg QD	-2	100 mg QD

Vactosertib dose can be reduced to manage a treatment related AE as indicated in Table 9.

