5.3.5 Monitoring and Management for AEs Associated with Vactosertib

Patients should receive appropriate supportive care measures as deemed necessary by the treating investigator. Suggested monitoring and dose modifications are for the management of a treatment related AE are outlined in Table 9. Refer to Table 6 in section 5.2 for vactosertib treatment levels.

Table 9 Vactosertib Dose Modifications for Treatment-Related Toxicity

Toxicity	Severity Grade	Vactosertib Dose Modification
Hematologic toxicity	1/2	Continue at the same Treatment Level
	3	Withhold until toxicity is Grade \leq 2, or has returned to baseline, then resume treatment at the same Treatment Level or reduce the dose by 1 Treatment Level after discussion with the Sponsor a
	4	Withhold until toxicity is Grade \leq 2, or has returned to baseline, then reduce by 1 Treatment Level
Non-hematologic toxicity and/or other drug related toxicities b	1	Continue at the same Treatment Level
	2	For persistent (>1-2 week) Grade 2 events, consider holding study drug until resolution to Grade \leq 1 or baseline. If the study drug is withheld and the toxicity resolved to Grade \leq 1 or baseline, resume treatment at the same Treatment Level or reduce by 1 Treatment Level
	3	Withhold until toxicity is Grade \leq 1, or has returned to baseline, then resume treatment at the same Treatment Level or reduce the dose by 1 Treatment Level after discussion with the Sponsor
	4	Discontinue vactosertib

ALT or AST elevation possibly related with total bilirubin <2x ULN	1	Continue at the same Treatment Level
	2	Continue at the same Treatment Level Repeat ALT or AST and total bilirubin within 7 days when subject is symptomatic; If not symptomatic, monitor weekly. For persistent (>1-2 week) Grade 2 events, consider holding study drug until resolution to Grade ≤1 or baseline. If the study drug is withheld and the toxicity resolved to Grade ≤1 or baseline, resume treatment at the same Treatment Level or reduce by 1 Treatment Level
	3/4	Withhold dose until toxicity is Grade ≤ 1, or has returned to baseline, then resume treatment by reducing by one Treatment Level. Repeat within 48~72 hours until resolution to Grade ≤1. If Grade 3 ALT or AST elevation recurs at dose level -2, then discuss with Sponsor whether to discontinue permanently.

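### Table 6 gives the same neoadjuvant vactosertib dose at levels -1 and -2, so a second one-level reduction does not lower the dose (minor)

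*Combined protocol and SAP*

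**What the plan says.** Table 6 (Section 5.2) sets the vactosertib levels:

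| Level | Neoadjuvant | Adjuvant |
|---|---|---|
| 0 | 200 mg QD | 200 mg BID |
| -1 | 100 mg QD | 200 mg QD |
| -2 | 100 mg QD | 100 mg QD |

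After the leading minus sign, the lower two rows read "1 100 mg QD -1 200 mg QD" and "2 100 mg QD -2 100 mg QD". No other section gives a different neoadjuvant dose for level -2.

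The two tables point to each other. Section 5.2 states "Vactosertib dose can be reduced to manage a treatment related AE as indicated in Table 9", and Section 5.3.5 states "Refer to Table 6 in section 5.2 for vactosertib treatment levels". Neither exempts the neoadjuvant phase.

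Three rows of Table 9 call for a one-level reduction with no option to resume at the same level:

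- Grade 4 hematologic toxicity: "then reduce by 1 Treatment Level".
- Grade 3/4 ALT or AST elevation with bilirubin below 2x ULN: "then resume treatment by reducing by one Treatment Level".
- Grade 2 ALT or AST elevation with bilirubin at or above 2x ULN: the same instruction.

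The second of these rows also says that a Grade 3 elevation recurring at dose level -2 should prompt a discussion with the sponsor about permanent discontinuation.

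**The concern.** A reduction level that carries the same dose as the level above it is a reduction in name only. Before surgery, a patient already at level -1 who meets one of the three rows would be moved down a level and resume at the same 100 mg QD.

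The ALT/AST row matters most. Its discontinuation prompt is tied to level -2. Read literally, a patient whose Grade 3 elevation recurs on 100 mg QD could be re-exposed to 100 mg QD before the table raises the question of stopping. This would happen shortly before a liver resection with curative intent.

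Liver toxicity is relevant to this combination. Section 1.2.2.3 reports a Grade 3 acute hepatitis among the 11 patients whose tolerability data led to the vactosertib dose decrease. That was at 300 mg BID, above the dose used here, so it shows the type of event but not how often to expect it.

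**Working it through.** **Step sizes.** Inputs are the Table 6 doses converted to mg/day (BID = 2 x 200 = 400). Change = (new - old)/old.

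| Phase | Level 0 to -1 | Level -1 to -2 |
|---|---|---|
| Neoadjuvant | (100 - 200)/200 = -50% | (100 - 100)/100 = 0% |
| Adjuvant | (200 - 400)/400 = -50% | (100 - 200)/200 = -50% |

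Only the second neoadjuvant step fails. The adjuvant column steps down normally and the rows are complete, so nothing in the text suggests a reading fault.

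**How many doses could be given at neoadjuvant level -2.** Inputs and assumptions:

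- Dosing is once daily, 5 days on and 2 off, for two weeks (Table 4, Section 5.1.2): 5 x 2 = 10 doses, on days 1-5 and 8-12. Section 3.4 says 20 doses, which does not fit its own once-daily schedule; 10 is used here.
- The first Grade 3 ALT/AST elevation is found on day *d*, and that day's dose is withheld.
- Each hold lasts 2 or 3 days. Table 9 gives only a repeat-test interval, "Repeat within 48~72 hours until resolution to Grade" 1 or below, and this is taken as the whole recovery time.
- The elevation recurs 1, 2 or 3 days after restarting at level -1. A second hold of the same length follows, then a restart at level -2.

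This gives 2 x 3 = 6 settings for each *d*. Restart falls on the first dosing day on or after *d* + hold. The second restart falls on the first dosing day on or after (first restart + recurrence interval + hold).

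| First elevation found on day | Doses left at level -2 (range over 6 settings) |
|---|---|
| 2 | 2 to 5 |
| 3 | 0 to 5 |
| 4, 5 or 6 | 0 to 2 |
| 7 | 0 to 1 |
| 8 or later | 0 in all 6 |

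Two examples:

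- *d* = 2, hold 2, recurrence after 1 day: restart day 4, recurrence day 5, hold to day 7 (a rest day), restart day 8, leaving days 8-12, or 5 doses.
- *d* = 8, hold 2, recurrence after 1 day: restart day 10, recurrence day 11, earliest restart day 13, after the last dosing day. None left.

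**When an elevation would be found.** The pre-surgical laboratory visit is 7 to 14 days after C1D1 (Section 6.1.3, Table 10), so day 8 or later, where the count is 0. If the general window of ±3 days in Section 6.1 is applied, the earliest is day 8 - 3 = day 5, giving 0 to 2 doses. Detection on days 2 to 4 needs an unscheduled test.

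All these figures are upper bounds, because a Grade 3 elevation would have to settle to Grade 1 or baseline within 2 or 3 days, twice.

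**The case against.** **Table 9 does not bind the investigator.** It is introduced with "Suggested monitoring and dose modifications are for the management of a treatment related AE are outlined in Table 9". Its last note allows other level changes or holds in discussion with the sponsor. Section 5.2 directs the lowest dose, or discontinuation if warranted, when several adverse events give conflicting advice. Section 6.4 lets the investigator discontinue treatment for any untoward effect. Section 6.1.4 lets surgery go ahead after an incomplete course unless there are safety concerns about the operation. All of this stands and keeps the point minor. It lets an investigator depart from the table but does not give level -2 a meaning.

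**The count ignores early surgery.** Table 10 allows surgery from 7 days after C1D1, and every non-zero count above consists of doses on days 8 to 12. Surgery near day 8 would remove most or all of them. This is correct and shrinks the reach further.

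**The late prompt depends on what was intended.** If a distinct, lower level -2 was meant, a correct table would still put the prompt at level -2, after the same number of re-exposures. The error would then be in the dose and not in the timing. As an illustration only, 50 mg is a supplied tablet strength (Section 4.1.2); at 50 mg QD the missing step would be (50 - 100)/100 = -50%. This is fair: the delay follows only if 100 mg QD was meant to be the lowest dose.

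**The repeated cell could be a deliberate floor.** That cannot be ruled out. A floor would still need saying, because Table 9 goes on to call for a reduction at level -1 and hangs its prompt on level -2.

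**Conclusion.** The point holds and is minor. As printed, the second neoadjuvant reduction is 0%, against 50% for each of the other three steps, and Table 9 relies on that level for an ALT/AST safety prompt. If 100 mg QD was meant as the floor, the wording of the table puts the discontinuation discussion after the second recurrence at 100 mg QD instead of the first. If a lower dose was meant, the patient resumes at a higher dose than intended.

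Under the stated hold and recurrence assumptions, exposure at level -2 is 0 doses when the elevation is found on day 8 or later, 0 to 2 on days 5 to 7, and 0 to 5 on days 2 to 4, out of 10 planned. The event would be very rare among at most 19 planned patients. The first neoadjuvant reduction and both adjuvant reductions work properly. The primary endpoint, the target of 17 evaluable patients and the power calculation do not depend on this table.

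The identical doses are certain from the text; the intended level -2 dose is not stated anywhere.

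**What to change.** Delete neoadjuvant level -2 from Table 6 and add a note to Table 9 along these lines:

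> In the neoadjuvant phase 100 mg QD (level -1) is the lowest dose. Toxicity that needs a further reduction at level -1 means stopping vactosertib or discussing discontinuation with the sponsor, and the Grade 3 ALT/AST recurrence trigger applies at level -1.

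If a distinct third neoadjuvant dose was intended, the sponsor should enter it in Table 6 instead; the trigger can then stay at level -2. The sponsor should confirm which reading is right before the text is changed.

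The cost is one table row and a two-sentence note. Section 9.4 requires protocol review committee and IRB approval of any amendment, so it is best carried in the next one. Endpoints, sample size and analyses do not change.

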5.3 Monitoring and Toxicity Management

Each patient receiving pembrolizumab-based treatment will be evaluable for safety. The safety parameters include all laboratory tests and hematological abnormalities, physical findings, and spontaneous reports of AEs reported to the investigator by patients.

Each patient will be assessed periodically for the development of any toxicity as outlined in 5.3.5. Toxicity will be assessed according to NCI CTCAE v5.0 (Appendix 3).

5.3.1 Toxicity Management for Immune-Related AEs Associated with Pembrolizumab

AEs associated with pembrolizumab exposure may represent an immune-related response. These irAEs may occur shortly after the first dose or several months after the last dose of pembrolizumab treatment and may affect more than one body system simultaneously. Therefore, early recognition and initiation of treatment is critical to reduce complications. Based on existing clinical study data, most irAEs were reversible and could be managed with interruptions of pembrolizumab, administration of corticosteroids and/or other supportive care. For suspected irAEs, ensure adequate evaluation to confirm etiology or exclude other causes. Additional procedures or tests such as bronchoscopy, endoscopy, skin biopsy may be included as part of the evaluation.

Dose modification and toxicity management guidelines for irAEs associated with pembrolizumab monotherapy, coformulations, or IO combinations are provided in Table 7.

Table 7 Dose Modification and Toxicity Management Guidelines for Immune-related Adverse Events Associated with Pembrolizumab Monotherapy, Coformulations and IO Combinations

General instructions:				

 1. Severe and life-threatening irAEs should be treated with IV corticosteroids followed by oral steroids. Other immunosuppressive treatment should begin if the irAEs are not controlled by corticosteroids. 2. Pembrolizumab monotherapy, coformulations, or IO combinations must be permanently discontinued if the irAE does not resolve or the corticosteroid dose is not \leq 10 mg/day within 12 weeks of the last study intervention treatment. 3. The corticosteroid taper should begin when the irAE is \leq Grade 1 and continue at least 4 weeks. 4. If pembrolizumab monotherapy, coformulations or IO combinations has been withheld, study intervention may resume after the irAE decreased to \leq Grade 1 after corticosteroid taper. 				

irAEs	Toxicity Grade (CTCAE v5.0)	Action With Pembrolizumab Monotherapy, Coformulations or IO Combinations	Corticosteroid and/or Other Therapies	Monitoring and Follow-up
Pneumonitis	Grade 2	Withhold	
 • Administer corticosteroids (initial dose of 1 to 2 mg/kg prednisone or equivalent) followed by taper • Add prophylactic antibiotics for opportunistic infections 	
 • Monitor participants for signs and symptoms of pneumonitis • Evaluate participants with suspected pneumonitis with radiographic imaging and initiate corticosteroid treatment
	Recurrent Grade 2, Grade 3 or 4	Permanently discontinue		
Diarrhea/Colitis	Grade 2 or 3	Withhold	
 • Administer corticosteroids (initial dose of 1 to 2 mg/kg prednisone or equivalent) 	
 • Monitor participants for signs and symptoms of enterocolitis (i.e., diarrhea,

irAEs	Toxicity Grade (CTCAE v5.0)	Action With Pembrolizumab Monotherapy, Coformulations or IO Combinations	Corticosteroid and/or Other Therapies	Monitoring and Follow-up
	Recurrent Grade 3 or Grade 4	Permanently discontinue	followed by taper	
abdominal pain, blood or mucus in stool with or without fever) and of bowel perforation (i.e., peritoneal signs and ileus)
 
 Participants with \geqGrade 2 diarrhea suspecting colitis should consider GI consultation and performing endoscopy to rule out colitis Participants with diarrhea/colitis should be advised to drink liberal quantities of clear fluids. If sufficient oral fluid intake is not feasible, fluid and electrolytes should be substituted via IV infusion
AST or ALT Elevation or Increased Bilirubin	Grade 2 ^a	Withhold	
 Administer corticosteroids (initial dose of 0.5 to 1 mg/kg prednisone or equivalent) followed by taper 	
 Monitor with liver function tests (consider weekly or more frequently until liver enzyme value returned to baseline or is stable)
	Grade 3 ^b or 4 ^c	Permanently discontinue	
 Administer corticosteroids (initial dose of 1 to 2 mg/kg prednisone or equivalent) followed by taper 	

irAEs	Toxicity Grade (CTCAE v5.0)	Action With Pembrolizumab Monotherapy, Coformulations or IO Combinations	Corticosteroid and/or Other Therapies	Monitoring and Follow-up
T1DM or Hyperglycemia	New onset T1DM or Grade 3 or 4 hyperglycemia associated with evidence of β -cell failure	Withhold ^d	
 Initiate insulin replacement therapy for participants with T1DM Administer antihyperglycemic in participants with hyperglycemia 	
 Monitor participants for hyperglycemia or other signs and symptoms of diabetes
Hypophysitis	Grade 2	Withhold	
 Administer corticosteroids and initiate hormonal replacements as clinically indicated 	
 Monitor for signs and symptoms of hypophysitis (including hypopituitarism and adrenal insufficiency)
	Grade 3 or 4	Withhold or permanently discontinue ^d		
Hyperthyroidism	Grade 2	Continue	
 Treat with nonselective beta-blockers (e.g., propranolol) or thionamides as appropriate 	
 Monitor for signs and symptoms of thyroid disorders
	Grade 3 or 4	Withhold or permanently discontinue ^d		
Hypothyroidism	Grade 2, 3 or 4	Continue	
 Initiate thyroid replacement hormones (e.g., levothyroxine or liothyronine) per standard of care 	
 Monitor for signs and symptoms of thyroid disorders
Nephritis: grading according to increased creatinine or acute kidney injury	Grade 2	Withhold	
 Administer corticosteroids (prednisone 1 to 2 mg/kg or equivalent) followed by taper 	
 Monitor changes of renal function
	Grade 3 or 4	Permanently discontinue		
Neurological Toxicities	Grade 2	Withhold	
 Based on severity of AE administer corticosteroids 	
 Ensure adequate evaluation to confirm etiology and/or exclude other causes
	Grade 3 or 4	Permanently discontinue		

irAEs	Toxicity Grade (CTCAE v5.0)	Action With Pembrolizumab Monotherapy, Coformulations or IO Combinations	Corticosteroid and/or Other Therapies	Monitoring and Follow-up
Myocarditis	Asymptomatic cardiac enzyme elevation with clinical suspicion of myocarditis (which was previously myocarditis Grade 1 using CTCAE v4.0)	Withhold	
 Based on severity of AE administer corticosteroids 	
 Ensure adequate evaluation to confirm etiology and/or exclude other causes
	Grade 2, 3 or 4	Permanently discontinue		
Exfoliative Dermatologic Conditions	Suspected SJS, TEN, or DRESS	Withhold	
 Based on severity of AE administer corticosteroids 	
 Ensure adequate evaluation to confirm etiology or exclude other causes
	Confirmed SJS, TEN, or DRESS	Permanently discontinue		
All Other irAEs	Persistent Grade 2	Withhold	
 Based on severity of AE administer corticosteroids 	
 Ensure adequate evaluation to confirm etiology or exclude other causes
	Grade 3	Withhold or discontinue based on the event ^e		
	Recurrent Grade 3 or Grade 4	Permanently discontinue		

irAEs	Toxicity Grade (CTCAE v5.0)	Action With Pembrolizumab Monotherapy, Coformulations or IO Combinations	Corticosteroid and/or Other Therapies	Monitoring and Follow-up

AE(s)=adverse event(s); ALT= alanine aminotransferase; AST=aspartate aminotransferase; CTCAE=Common Terminology Criteria for Adverse Events; DRESS=Drug Rash with Eosinophilia and Systemic Symptom; GI=gastrointestinal; IO=immuno-oncology; ir=immune related; IV=intravenous; SJS=Stevens-Johnson Syndrome; T1DM=type 1 diabetes mellitus; TEN=Toxic Epidermal Necrolysis; ULN=upper limit of normal.
 
Note: Non-irAE will be managed as appropriate, following clinical practice recommendations.
 
 a AST/ALT: >3.0 to 5.0 × ULN if baseline normal; >3.0 to 5.0 × baseline, if baseline abnormal; bilirubin:>1.5 to 3.0 × ULN if baseline normal; >1.5 to 3.0 × baseline if baseline abnormal b AST/ALT: >5.0 to 20.0 × ULN, if baseline normal; >5.0 to 20.0 × baseline, if baseline abnormal; bilirubin:>3.0 to 10.0 × ULN if baseline normal; >3.0 to 10.0 × baseline if baseline abnormal c AST/ALT: >20.0 × ULN, if baseline normal; >20.0 × baseline, if baseline abnormal; bilirubin: >10.0 × ULN if baseline normal; >10.0 × baseline if baseline abnormal d The decision to withhold or permanently discontinue pembrolizumab monotherapy, coformulations or IO combinations is at the discretion of the investigator or treating physician. If control achieved or ≤ Grade 2, pembrolizumab monotherapy, coformulations, or IO combinations may be resumed. e Events that require discontinuation include, but are not limited to: encephalitis and other clinically important irAEs (e.g., vasculitis and sclerosing cholangitis). 				

5.3.2 Toxicity Management of Infusion-Reactions Related to Pembrolizumab

Pembrolizumab may cause severe or life threatening infusion-reactions including severe hypersensitivity or anaphylaxis. Signs and symptoms usually develop during or shortly after drug infusion and generally resolve completely within 24 hours of completion of infusion. Dose modification and toxicity management guidelines on pembrolizumab-associated infusion reaction are provided in Table 8.

Table 8 Pembrolizumab Infusion Reaction Treatment Guidelines

NCI CTCAE Grade	Treatment
Grade 1 Mild reaction; infusion interruption not indicated; intervention not indicated	Increase monitoring of vital signs as medically indicated until the patient is deemed medically stable in the opinion of the investigator.
Grade 2 Requires therapy or infusion interruption but responds promptly to symptomatic treatment (e.g., antihistamines, NSAIDs, narcotics, IV fluids); prophylactic medications indicated for ≤24 hrs.	
Stop Infusion.
 
Additional appropriate medical therapy may include but is not limited to:
 
 IV fluids Antihistamines NSAIDs Acetaminophen Narcotics 
Increase monitoring of vital signs as medically indicated until the patient is deemed medically stable in the opinion of the investigator.
 
If symptoms resolve within 1 hour of stopping drug infusion, the infusion may be restarted at 50% of the original infusion rate (e.g. from 100 mL/hr. to 50 mL/hr.). Otherwise dosing will be held until symptoms resolve and the patient should be premedicated for the next scheduled dose.
 
Patients who develop Grade 2 toxicity despite adequate premedication should be permanently discontinued from further study drug treatment

Grades 3 or 4 Grade 3: Prolonged (i.e., not rapidly responsive to symptomatic medication and/or brief interruption of infusion); recurrence of symptoms following initial improvement; hospitalization indicated for other clinical sequelae (e.g., renal impairment, pulmonary infiltrates) Grade 4: Life-threatening; pressor or ventilatory support indicated	
Stop Infusion.
 
Additional appropriate medical therapy may include but is not limited to:
 
 Epinephrine** IV fluids Antihistamines NSAIDs Acetaminophen Narcotics Oxygen Pressors Corticosteroids 
Increase monitoring of vital signs as medically indicated until the patient is deemed medically stable in the opinion of the investigator.
 
Hospitalization may be indicated.
 
**In cases of anaphylaxis, epinephrine should be used immediately.

NCI CTCAE Grade	Treatment
Patient is permanently discontinued from further study drug treatment.	
Abbreviations: CTCAE = Common Terminology Criteria for Adverse Events; IV = intravenous; NCI = National Cancer Institute; NSAIDs = non-steroidal anti-inflammatory drugs; PO = by mouth.	
Appropriate resuscitation equipment should be available at the bedside and a physician readily available during the period of drug administration. For further information, please refer to the CTCAE v5.0 at http://ctep.cancer.gov	

